### **3.1.3 Safety Monitoring Committee**

In Part 1, the safety of combination treatment will be evaluated by a Safety Monitoring Committee (SMC) prior to expansion of enrollment to evaluate treatment effect in Part 2, as detailed in Section [9.3.9](#). In Part 1, after 6 patients have been followed through the end of the dose-limiting toxicity (DLT) period, or at the point that 2 or more patients experience a DLT, whichever comes first, the SMC will review all available data and make a recommendation for one of the following:

1. To proceed to Part 2 of the study, expanding enrollment with additional patients treated with the study drugs at the doses and schedule determined to be safe in Part 1 of the study
2. To repeat Part 1 of the study and treat up to 6 additional patients at the same drug doses and schedule previously tested or with any of the following modifications that may include, but are not limited to:
  - a. Dose reduction of brentuximab vedotin to 1.2 mg/kg and/or nivolumab to 1 mg/kg; of note, doses may not be increased above 1.8 mg/kg brentuximab vedotin or 3 mg/kg nivolumab
  - b. Administration of combination treatment on Day 1 of every cycle
3. To close the study to additional enrollment.

Part 2 of the study will further characterize safety and evaluate the antitumor activity of brentuximab vedotin combined with nivolumab in patients who have failed standard frontline chemotherapy by enrolling approximately 50 additional patients at the recommended dose schedule determined in Part 1.

Part 3 of the study will further characterize safety and efficacy of the study drug combination administered as same-day dosing in all cycles by enrolling approximately 30 additional patients with relapsed or refractory HL at the recommended doses as followed in Part 2. If any safety signals are observed after the first 6 patients in Part 3 have been treated for 2 cycles, then an SMC meeting will be convened.

Details of the SMC will be documented in an SMC charter.

### **3.1.4 Dose-Limiting Toxicities**

DLTs are only assessed during Part 1 of the study. For the purpose of this study, DLTs are defined as any study drug-related toxicity (brentuximab vedotin or nivolumab) that requires either a dose reduction or delay of more than 7 days of either study drug in Cycle 2 or delays the Cycle 3 Day 1 administration of combined treatment by more than 7 days. The DLT-evaluation period consists of the first cycle of therapy through the Cycle 3 Day 1 administration of combined treatment. The Investigator's Brochures for brentuximab vedotin and nivolumab individually describe AEs commonly observed relative to either agent (i.e., neutropenia or peripheral neuropathy with brentuximab vedotin; immune-mediated AEs with nivolumab), as well as less common serious findings. The respective Investigator's Brochures should be referenced when attributing causality; however, the final decision regarding causality is at the discretion of the investigator.

If any patient enrolled in Part 1 discontinues the study during the DLT period, that patient will be replaced unless discontinuation is for DLT.

## **3.2 Discussion and Rationale for Study Design**

The endpoints of this study are appropriate for evaluating the safety of brentuximab vedotin treatment in combination with nivolumab for patients with relapsed or refractory HL. The DLT evaluation in Part 1 of the study will provide an opportunity to assess safety and tolerability of combination treatment, the components of which have previously been assessed for safety in other settings. Expanded enrollment in Part 2 is designed to assess the efficacy of the combination treatment based on CR rate with staggered dosing of nivolumab and to provide additional safety data. The sample size is chosen to provide satisfactory power to exclude the previously demonstrated CR rate of single-agent brentuximab vedotin in a similar patient population in the case that the true CR rate of the combination treatment meets a clinically compelling threshold.

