**Statistical Methods**

Safety and efficacy analyses will be summarized with descriptive statistics. Frequencies and percentages will be used when presenting categorical variables. The primary efficacy endpoint of CR rate will be tested using a one-sided exact binomial test with a null hypothesis of CR rate less than or equal to 30% and  $\alpha=0.05$ .

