### 1.3.1 Brentuximab Vedotin

Brentuximab vedotin is a CD30-directed antibody-drug conjugate (ADC) consisting of 3 components: 1) the chimeric IgG1 antibody cAC10, specific for human CD30; 2) the microtubule-disrupting agent monomethyl auristatin E (MMAE); and 3) a protease-cleavable linker that covalently attaches MMAE to cAC10. The primary mechanism of anticancer activity of brentuximab vedotin is binding of the ADC to CD30-expressing cells, followed by internalization of the ADC-CD30 complex, and the release of MMAE via proteolytic cleavage. Binding of MMAE to tubulin disrupts the microtubule network within the cell, subsequently inducing cell cycle arrest and apoptotic death of the cell. Possible additional mechanisms of anticancer activity include bystander effects on nearby cells in the tumor microenvironment, immunogenic cell death, and antibody-dependent cellular phagocytosis ([Oflazoglu 2007](#); [Li 2014](#); [Muller 2014](#); [Gardai 2015](#); [Kim 2015](#)).

In a pivotal phase 2 study of 102 patients with relapsed or refractory HL following autologous stem cell transplant (ASCT), treatment with brentuximab vedotin 1.8 mg/kg every 3 weeks resulted in an objective response rate (ORR) of 75% (95% confidence interval [CI], 64.9%–82.6%). The complete response (CR) rate was 34% (95% CI, 25.2%–44.4%) and the median progression-free survival (PFS) for all patients on study was 5.6 months (95% CI, 5.0–9.0 months) ([Younes 2012](#)).

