The activity of brentuximab vedotin in patients who had previously received it was demonstrated in the SGN35-006 study of patients with hematologic malignancies who initially responded to brentuximab vedotin and then subsequently progressed ([Bartlett 2014](#)). In this open-label, multicenter, phase 2 study of patients with HL or systemic anaplastic large cell lymphoma who had responded to brentuximab vedotin monotherapy during a previous clinical trial ([Bartlett 2014](#)), patients were eligible if they had achieved a partial response (PR) or better to initial treatment with brentuximab vedotin, discontinued treatment while in remission, and subsequently developed disease progression or relapse. In the retreatment study, patients received brentuximab vedotin 1.8 mg/kg on Day 1 of each 21-day treatment cycle. Patients whose dose was reduced to 1.2 mg/kg for any reason during their initial therapy were given 1.2 mg/kg on Day 1 of each 21-day treatment cycle upon retreatment. Of the 21 patients with HL enrolled, the median time between the last brentuximab vedotin dose from initial treatment and the first dose at retreatment was 11.4 months (range 4–45 months). The ORR and CR rates with brentuximab vedotin retreatment were 60% and 30%, respectively. The median duration of response was 9.2 months (range 0.0+ to 19.5+ months). For patients who achieved a CR, the median duration of response was 9.4 months (range 1.7–14.2 months). The median PFS was 9.9 months, and the median overall survival (OS) had not been reached at the time of study closure. The most common adverse events (AEs) were peripheral sensory neuropathy (59%), fatigue and nausea (41% each), diarrhea (38%), and

arthralgia, headache, peripheral motor neuropathy, and pyrexia (28% each). The most common AEs that were  $\geq$  Grade 3 consisted of anemia (17%), fatigue (14%), and hyperglycemia, hypophosphatemia, and thrombocytopenia (10% each). No serious AEs leading to death were attributed to brentuximab vedotin.

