#### **4.2 Exclusion Criteria**

1. Patient has received prior salvage therapy, including salvage radiotherapy, for relapsed or refractory classical HL
2. Chemotherapy or biologics therapy that is not completed 4 weeks prior to the first dose of study drug(s), unless documented progression of underlying disease on treatment
3. Prior radiation therapy within 3 weeks, or chest radiation  $\leq 12$  weeks prior to first dose of the study drug(s)
4. For patients in Parts 1 and 2, previous treatment with brentuximab vedotin; for Part 3, patients with HL that is refractory to a brentuximab vedotin-containing regimen in first line, or patients who discontinue brentuximab vedotin due to unacceptable toxicity are ineligible. Refractory disease is defined as never achieving a CR to frontline therapy or having a CR but then progressing within 3 months of completing frontline therapy
5. Has received any prior immuno-oncology therapy (e.g., therapies affecting the PD-1, CTLA4, or CD137 pathways)
6. Previously received an allogeneic and/or autologous stem cell transplant for HL
7. Current therapy with other systemic antineoplastic or investigational agents
8. Systemic treatment with either corticosteroids ( $>10$  mg daily prednisone equivalent) or other immunosuppressive medications within 14 days of enrollment
  - Inhaled or topical steroids and adrenal replacement steroid doses  $>10$  mg daily prednisone equivalent, are permitted in the absence of active autoimmune disease
9. History of another primary invasive malignancy that has not been in remission for at least 3 years
10. History of progressive multifocal leukoencephalopathy (PML)

11. Known cerebral/meningeal disease related to the underlying malignancy
12. Pre-existing neuropathy of Grade 2 or greater
13. Any active Grade 3 or higher (per the National Cancer Institute's Common Terminology Criteria for Adverse Events [NCI CTCAE], Version 4.03) viral, bacterial, or fungal infection within 2 weeks prior to the first dose of brentuximab vedotin; routine antimicrobial prophylaxis is permitted
14. Females who are pregnant or breastfeeding
15. Known hypersensitivity to any excipient contained in the drug formulation of brentuximab vedotin or nivolumab
16. Positive for hepatitis B by surface antigen expression, or any other positive test for hepatitis B virus indicating acute or chronic infection

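### Does testing against a 30% CR rate fall short of the single-agent benchmark that Protocol 3.2 says the sample size can exclude?

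*Protocol*

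**What the plan says.** Protocol 3.2 explains the sample size by its purpose: to have "satisfactory power to exclude the previously demonstrated CR rate of single-agent brentuximab vedotin in a similar patient population", and this "in the case that the true CR rate of the combination treatment meets a clinically compelling threshold". It gives a value for neither the benchmark nor the threshold.

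The test itself is fully specified. The synopsis says the CR rate "will be tested using a one-sided exact binomial test with a null hypothesis of CR rate less than or equal to 30" per cent. Protocol 9.1 and 9.3.5.1 and SAP 6.2 and 7.5.1.1 use the same null at one-sided alpha 0.05. Protocol 9.1 and SAP 6.2 require at least 53 patients, reject at 22 or more CRs, and claim roughly 90% power at a true rate of 50%. None of these sections gives a basis for 30%.

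Protocol 1.3.1 reports two CR rates for brentuximab vedotin alone:

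- The first begins "In a pivotal phase 2 study of 102 patients with relapsed or refractory HL following autologous stem cell transplant (ASCT"); there, "The complete response (CR) rate was 34" per cent, with a 95% CI of 25.2% to 44.4%.
- The second is from patients treated with the drug again: "The ORR and CR rates with brentuximab vedotin retreatment were 60% and 30%, respectively". That study enrolled 21 patients with HL.

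The exclusion criteria in Protocol 4.2 rule out both kinds of patient from the tested population: "Previously received an allogeneic and/or autologous stem cell transplant for HL" (all parts) and "For patients in Parts 1 and 2, previous treatment with brentuximab vedotin".

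**The concern.** In a single-arm trial, the meaning of a positive result depends on the external reference rate. Section 3.2 says that reference is what brentuximab vedotin achieves alone. The only first-exposure figure in the protocol is 34%, and the null is 30%. Read together, these suggest that the trial could reject its null, and be described as having beaten the single agent, on data that do not exclude 34%. If the true combination rate were exactly 34%, the planned rule would still be met 15.6% of the time. At stake would be the interpretation of a marginal result and the truth of the power statement in 3.2.

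**Working it through.** **Inputs.** Null 0.30, alternative 0.50, one-sided alpha 0.05, n = 53, rejection at 22 or more CRs (Protocol 9.1, SAP 6.2). Cited single-agent rate 34%, 95% CI 25.2% to 44.4% (Protocol 1.3.1). Two-sided 90% exact interval (Protocol 9.3.5.1). Interim result 18/29 (Protocol 3.2.1).

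**Step 1: the plan's own figures.** With X binomial(53, p):

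- P(X ≥ 22 | p = 0.30) = 0.0495 and P(X ≥ 21 | p = 0.30) = 0.0862, so 22 is the smallest count that rejects.
- P(X ≥ 22 | p = 0.50) = 0.9155, which matches the stated power of about 90%.
- 22/53 = 41.5%, as stated.

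No smaller n reaches 90% power (52 patients give 0.894). Every figure for the 30% null is right.

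**Step 2: the same counts against 34%.** The one-sided p-value is P(X ≥ x | 53, p₀). The lower limit L of the 90% exact interval solves P(X ≥ x | 53, L) = 0.05, so L exceeds p₀ exactly when the p-value is below 0.05.

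| CRs of 53 | p against 30% | p against 34% | Lower 90% limit |
|---|---|---|---|
| 22 | 0.0495 | 0.156 | 30.0% |
| 23 | 0.0266 | 0.098 | 31.8% |
| 24 | 0.0134 | 0.058 | 33.5% |
| 25 | 0.0063 | 0.032 | 35.3% |

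The ambiguous range is therefore 22 to 24 CRs.

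**Step 3: power against 34%.** The critical count is 25, and P(X ≥ 25 | 53, p) depends on the true rate:

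- p = 0.50: 70.8%
- p = 0.55: 90.0%
- p = 0.60: 97.9%

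The 70.8% comes from combining 3.2 with the 50% alternative in 9.1. Section 3.2 does not make that pairing, because it leaves its threshold without a value. For a threshold of about 55% or more, the power claim would hold even against 34%.

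**Step 4: is 34% the benchmark that 3.2 means?** Section 3.2 speaks of a similar population.

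| Cited rate | Patients | Eligible for Parts 1 and 2? |
|---|---|---|
| 34% | Relapsed or refractory after ASCT | No, prior transplant is excluded |
| 30% | Retreated with brentuximab vedotin | No, prior brentuximab vedotin is excluded |

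Neither figure is tied to the null, and neither population matches. The 34% is itself imprecise. At n = 53 and a true rate of 50%, taking its lower CI limit (25.2%) as the benchmark gives 97.3% power, and taking its upper limit (44.4%) gives 20.5%. A null of 30% lies inside that CI.

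**Step 5: how likely is a result in the ambiguous range?** Assume that all 29 interim patients belong to the primary set and that the 18 CRs stand. Parts 1 and 2 could total 53 (the stated minimum), 55 (the planned number) or 56 (6 + 50), leaving 24, 26 or 27 patients. The ambiguous ranges are 22–24 of 53, 23–25 of 55 and 24–25 of 56, so the remaining patients would have to supply 4–6, 5–7 or 6–7 CRs.

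| True rate in remaining patients | n = 53 | n = 55 | n = 56 |
|---|---|---|---|
| 40% | 9.2% | 11.5% | 8.0% |
| 50% | 1.1% | 1.4% | 0.9% |
| 62% | 0.03% | 0.03% | 0.01% |

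For example, at 50% with 24 remaining: [C(24,4) + C(24,5) + C(24,6)] / 2²⁴ = (10,626 + 42,504 + 134,596) / 16,777,216 = 0.0112.

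**The case for a change.** The best argument for a change is traceability. Section 3.2 is where the protocol says what the sample size is meant to show. It calls its comparator demonstrated and its population similar, and it supports neither word with a figure or a citation. The one first-exposure rate that a reader can find is above the null. The retreatment figure of 30% is not offered as the source: according to the Amendment 4 log, that study was added to justify enrolling previously treated patients in Part 3. Rewording 3.2 would cost almost nothing and would alter no test, threshold or analysis.

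Part of this stands. The basis for 30% is not stated, and a clause giving it would help readers. It does not amount to a fault in the plan, for three reasons:

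- A contradiction needs 3.2 to mean 34%, and the documents do not establish that.
- The protection that a reader needs is already planned. The null is explicit, the 90% exact interval is reported with the test, and SAP 7.5.1.1 adds a 95% exact interval. If 34% is not excluded, the result will show it. No objective in Protocol section 2 claims a comparison with single-agent brentuximab vedotin.
- The obvious rewording, a disclaimer about 34%, would give protocol standing to a benchmark from patients this trial does not enroll, and it would still leave the source of 30% blank.

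**Conclusion.** No change is needed. The protocol leaves its reference rate unreferenced in 3.2, but the hypothesis that is tested is unambiguous and its operating characteristics are correct: exact alpha 0.0495 and power 91.6% at n = 53. The shortfall against 34% is real as arithmetic (22 to 24 CRs of 53; 70.8% power at a true rate of 50%). It would matter only if 34% were the intended benchmark and 50% the intended threshold, and the documents establish neither. On the interim result, a final count in the ambiguous range has a probability of 0.9% to 1.4% if the remaining patients respond at 50%, and 8.0% to 11.5% if they respond at 40%. This rests on the 29 interim patients all counting in the primary set with their responses unchanged. According to SAP section 4, enrollment to Parts 1 and 2 was complete before Part 3 was added, so conduct is not affected either. Stating the basis for 30% would be an optional courtesy to readers and would alter no analysis or conclusion.

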### **3.2.1 Rationale for Study Design of Same-day Dosing**

On interim analysis, patients in Parts 1 and 2 had an ORR of 90% (95% CI 72.6%, 97.8%; 26/29 patients) and a CR rate of 62% (95% CI 42.3%, 79.3%; 18/29 patients). Similar results were reported by the ECOG-ACRIN Cancer Research Group study (E4412 Arms D and E) (ORR 100%, 8/8 evaluable patients; CR rate 62.5%, 5/8 patients), which enrolled patients with relapsed refractory HL for treatment with both brentuximab vedotin and nivolumab on Day 1 beginning with Cycle 1 ([Diefenbach 2016](#)). Based on results from both studies, a decision was made to amend the protocol to evaluate the safety and efficacy of same-day dosing of the study-drug combination beginning with Cycle 1. This new cohort, Part 3, will enroll patients with relapsed or refractory HL and will permit patients previously treated with brentuximab vedotin to explore activity of the combined regimen in brentuximab vedotin-exposed patients.

### **3.2.2 Method of Assigning Patients to Treatment Groups**

In this open-label study, each part of the trial will enroll sequentially. Enrollment and treatment in Part 1 will be completed before enrollment begins in Part 2, which will evaluate a staggered dosing schedule of brentuximab vedotin and nivolumab in Cycle 1 followed by same-day dosing of both drugs in Cycles 2 through 4.

After enrollment in Part 2 is complete, approximately 30 patients will be enrolled in Part 3 to evaluate same-day dosing of brentuximab vedotin and nivolumab in all treatment cycles.

### **3.2.3 Rationale for Selection of Doses**

The recommended dose for brentuximab vedotin per its prescribing information is 1.8 mg/kg via intravenous (IV) infusion administered every 3 weeks. This dose and schedule were evaluated in two pivotal phase 2 studies (SG035-0003 and SG035-0004) in patients with CD30-positive hematologic malignancies. This dose and schedule for retreatment with brentuximab vedotin monotherapy were similarly evaluated in a separate phase 2 study (SGN35-006) with the caveat that patients enrolled for retreatment who had a dose reduction for any reason to 1.2 mg/kg during their initial therapy would receive brentuximab vedotin retreatment at the reduced dose of 1.2 mg/kg.

The dose for nivolumab for this study is 3 mg/kg via IV infusion administered every 3 weeks. The approved dose for nivolumab as monotherapy is 3 mg/kg every 2 weeks for the treatment of melanoma and metastatic squamous non-small cell lung cancer. However, nivolumab has been studied as monotherapy and in combination treatment in several tumor types with dosing every 3 weeks. It was recently reported that nivolumab dose levels of 0.3, 2, and 10 mg/kg every 3 weeks yielded similar ORR, PFS, and OS in a phase 2 trial of patients with metastatic renal cell carcinoma ([Motzer 2015](#)). Moreover, nivolumab dose levels of 0.1, 0.3, 1, 3, and 10 mg/kg every 2 weeks were associated with very similar (median 64%–70%) PD-1 receptor occupancy and comparable ORR and PFS in patients with advanced melanoma ([Topalian 2012](#)). These findings indicate a flat dose-response relationship for nivolumab across a wide dose range for both 2- and 3-week dosing schedules, suggesting that dosing nivolumab at 3 mg/kg every 3 weeks is appropriate in the current study. These results further suggest that reduction of the nivolumab dose level to 1 mg/kg every 3 weeks is appropriate if the combination of 3 mg/kg nivolumab with brentuximab vedotin results in an unfavorable safety profile.

The rationale for staggered dosing of brentuximab vedotin and nivolumab in Cycle 1 is supported by the reasoning that, by delivering brentuximab vedotin, a directly cytotoxic agent, 1 week prior to nivolumab in Cycle 1, it is anticipated that tumor-associated antigens will be released and available for presentation to resident cytotoxic T cells at the same time that these cells become activated through PD-1 blockade. However, because of the long half-life of nivolumab, there is no rationale to continue staggered dosing beyond Cycle 1.

Same-day dosing in all treatment cycles is supported by data from the ECOG-ACRIN study (E4412) ([Diefenbach 2016](#)). In that study, patients in Arms D and E with relapsed or refractory HL were treated with brentuximab vedotin and nivolumab administered on Day 1

of 21-day cycles. The regimen was well-tolerated in the 10 patients who were evaluable for safety, with only 1 infusion-related reaction observed. The ORR was 100% in 8 efficacy-evaluable patients, with a CR rate of 62.5%. Based on the low rate of infusion-related reactions and promising activity observed in the E4412 study, the protocol was amended to explore same-day dosing in Part 3 of the SGN35-025 study.

### **3.2.4 Blinding**

This is an open-label study. Blinding will not be implemented.

## **4 STUDY POPULATION**

Patients must meet all of the enrollment criteria to be eligible for this study. Eligibility criteria may not be waived by the investigator and are subject to review in the event of good clinical practice (GCP) audit and/or health regulatory authority inspection.

### **4.1 Inclusion Criteria**

1. Documented histopathological diagnosis of classical HL, excluding nodular lymphocyte-predominant Hodgkin lymphoma (NLPHL)
2. Patients must have biopsy-proven (see Section 6.2) relapsed or refractory disease after failure of standard frontline chemotherapy for the treatment of classical HL
  - Relapsed disease is defined as achieving a CR to frontline therapy but then progressing 3 months or more after completing frontline therapy
  - Refractory disease is defined as never achieving a CR to frontline therapy or having a CR but then progressing within 3 months of completing frontline therapy
3. Patients must have fluorodeoxyglucose positron emission tomography- (FDG-PET) avid and bidimensional measureable disease of at least 1.5 cm in longest axis as documented by radiographic technique (spiral computed tomography [CT] preferred)
4. Patients must have confirmation of diffusing capacity of the lung for carbon monoxide (DLCO) over 60% (adjusted for hemoglobin) by a pulmonary function test
5. Age 18 years and older
6. An Eastern Cooperative Oncology Group (ECOG) performance status score of 0–1
7. Patients must be considered eligible to undergo autologous stem cell transplant
8. Patients must have the following required baseline laboratory data:
  - Absolute neutrophil count (ANC)  $\geq 1000/\mu\text{L}$
  - Platelet count  $\geq 50,000/\mu\text{L}$  (no platelet transfusions for prior 14 days)
  - Hemoglobin  $\geq 8.5 \text{ g/dL}$  (no red blood cell [RBC] transfusions for prior 7 days)
  - Serum bilirubin  $\leq 1.5 \times$  upper limit of normal (ULN) (except patients with Gilbert Syndrome, who can have total bilirubin  $< 3.0 \times$  ULN)
  - Alanine aminotransferase (ALT) and aspartate aminotransferase (AST)  $\leq 2.5 \times$  ULN

- Calculated creatinine clearance of  $\geq 30$  mL/min

9. Females of childbearing potential must have a negative serum or urine beta human chorionic gonadotropin ( $\beta$ -hCG) pregnancy test result within 7 days prior to the first dose of brentuximab vedotin. Females with false positive results and documented verification that the patient is not pregnant are eligible for participation. Females of non-childbearing potential are those who are postmenopausal greater than 1 year or who have had a bilateral tubal ligation or hysterectomy
10. Females of childbearing potential and males who have partners of childbearing potential must agree to use 2 effective contraceptive methods during the study and for 6 months following the last dose of brentuximab vedotin or 8 months following the last dose of nivolumab, whichever is later
11. Patients or their legally authorized representative must provide written informed consent

